7.1 Pre-operative Evaluation (-180 Days to Date of Surgery)

The following data will be collected from the pre-operative evaluation:

- Informed Consent
- Study Visit (CRF detailing type of visit and subject status)
- Eligibility
- Randomization
- Demographics
- Targeted Medical History (self-reported by subject or within clinic notes)
- Height and Weight (Collected on Vital Signs CRF)
- Narcotic Drug Use (patient reported)
- Preoperative Hip Evaluation (HE1)
- Harris Hip Score
- Radiographs (AP Hip (unilateral), AP Pelvis (bilateral), and Lateral)
- EQ-5D-5L
- Preoperative Planning Details (planned inclination and anteversion, planned cup & stem size)
- **OPTIONAL:** Preoperative templates (used for planning cup position, cup & stem size) Note: The Sponsor is requesting submission of preoperative templates, to be included with the preoperative radiographs, if the surgeon/site templates per their standard of care. Templating is not a requirement for participation in the study
- Protocol Deviation Form (if needed)

Confidential Version Date: 040CT2021

DePuy Synthes Protocol DSJ_2019_03 / Version 2.0 / TV-eFRM-02920 End of Study (Withdrawal) Case Report Form (if needed)

7.2 Operative and Perioperative Evaluation (Day 0 to Day of Discharge)

The following data will be collected from the operative and perioperative evaluations:

- Study Visit (CRF detailing type of visit and subject status)
- Operative Details
- Device Details
- Discharge Details
- Narcotic Drug Use (patient reported)
- Adverse Event Form (if needed)
- Protocol Deviation Form (if needed)
- Device Deficiency (if needed)
- End of Study (Withdrawal) Case Report Form (if needed)

7.3 Six Week Postoperative Evaluation (Day 14 – Day 60)

The following data will be collected from six-week postoperative evaluation:

- Study Visit (CRF detailing type of visit and subject status)
- Postoperative Hip Evaluation (HE2)
- Postoperative Hip Evaluation Functional Outcomes (HE3*)
- Narcotic Drug Use (patient reported)
- Harris Hip Score
- Radiographs (AP Hip (unilateral), AP Pelvis (bilateral), and Lateral)
- EQ-5D-5L
- Forgotten Joint Score
- Adverse Event Form (if needed)
- Protocol Deviation Form (if needed)
- Device Deficiency (if needed)
- End of Study (Withdrawal) Case Report Form (if needed)

* The Functional Outcomes portion of the Hip Evaluation CRF (HE3) will be initially completed at the 6 week visit, and only questions that are marked as "still cannot do" or "still have not returned to work" will be addressed at subsequent study visits

7.4 Twenty-Four Week Postoperative Evaluation (Day 61 to Day 200)

The following data will be collected from twelve-week postoperative evaluation:

- Study Visit (CRF detailing type of visit and subject status)
- Postoperative Hip Evaluation (HE2)
- Postoperative Hip Evaluation Functional Outcomes (HE3*)
- Narcotic Drug Use (patient reported)
- Harris Hip Score
- Radiographs (AP Hip (unilateral), AP Pelvis (bilateral), and Lateral)

EQ-5D-5L

Confidential Version Date: 040CT2021 DePuy Synthes Protocol DSJ_2019_03 / Version 2.0 / TV-eFRM-02920

- Forgotten Joint Score
- Adverse Event Form (if needed)
- Protocol Deviation Form (if needed)
- Device Deficiency (if needed)
- End of Study (Withdrawal) Case Report Form (required unless completed previously)

* The Functional Outcomes portion of the Hip Evaluation CRF (HE3) will be initially completed at the 6 week visit, and only questions that are marked as "still cannot do" or "still have not returned to work" will be addressed at subsequent study visits

7.5 Study Completion

A study completion CRF should be completed for each subject for the following reasons (list may not be inclusive of all reasons for study withdrawal):

- 1) Subject withdraws consent
- 2) Subject has the cup and/or stem revised or removed
- 3) All data is entered onto the CRFs as completely as possible and the Subject completes study per protocol
- 4) Subject dies
- 5) Subject is lost to follow up
- 6) Subject is a screen failure after consenting as described in section 3.5
- 7) Subject is withdrawn by the Investigator

8 Adverse Events (AEs)

An adverse event (AE) is defined as an untoward medical occurrence, unintended disease or injury, or untoward clinical signs (or change or worsening of a pre-existing medical condition) in a patient, which may or may not have an association with the device. In addition, an adverse device effect is defined as "any untoward and unintended response to a medical device". Further types of AEs and definitions are located in **Table 8-1** below.

For this study, there are three types of events that will need to be reported via the Adverse Events (AE) eCRF:

1) Device Related AEs (see Section 8.3 and Figure 8-1 below)

Confidential Version Date: 04OCT2021

DePuy Synthes Protocol DSJ_2019_03 / Version 2.0 / TV-eFRM-02920 Page **25** of **53**

- 2) Procedure Related AEs (see Section 8.4 and Figure 8-1 below)
- 3) Serious AEs (See Table 8-1 and Figure 8-1 below)

A record of each reportable adverse event, including details of the nature, onset, duration, severity, seriousness, relationship to the device, relationship to the operative procedure and outcome, will be made on an Adverse Events eCRF. Subjects must be questioned about any adverse event(s) at each subsequent encounter, whether a protocol scheduled follow up visit or not. The date that the site first became aware of the Subject's adverse event will also be documented (i.e., "site awareness date"). "Site awareness" is defined as the time when medical personnel and/or the site's study team, who are employed by or otherwise formally affiliated with the site (i.e., clinic and/or the hospital entity utilizing the same EMR system), obtain information about a reportable event.

AEs should be reported beginning from the start of surgery (*i.e.,* first incision) until Subject participation has ended (study completed, or consent withdrawn). When a Subject ends participation in the trial (either study completion or consent withdrawal) all open AE outcomes must be designated as "Recovered/Resolved with no residual effects", "Recovered/Resolved with residual effects", "Ongoing", "Death", or "Unknown" providing a resolution date or ongoing designation.

8.1 Anticipated Adverse Events / Non-Reportable Adverse Events (to Sponsor ONLY)

There are particular immediate non-serious post-operative events that are changes from the baseline condition of the Subject but are expected events resulting from surgery. For the purposes of this protocol these are referred to as Anticipated Adverse Events and are listed in Exhibit A. If these events occur, they should be recorded in the Subject's medical record, but these should NOT be reported as AEs in the eCRF or to the Sponsor. However, if these events occur with a severity deemed above "expected/normal" or meet the criteria of "serious", they should be reported to the Sponsor by completing an AE eCRF in the study database.

Table 8-1 Definitions of Adverse Event (AE) Types, Device Deficiency		
Adverse Event (AE)	AE is defined as an untoward medical occurrence, unintended disease or injury, or untoward clinical signs (or change or worsening of a pre-existing medical condition) in a patient, which may or may not have an association with the device.	
	All reported AEs (defined in Section 8) will be submitted to the DePuy Synthes Complaint Handling Unit, via electronic reporting from the AE eCRF, who will complete all reporting determinations.	
Serious Adverse Event (SAE)	 SAE is defined as an Adverse Event, regardless of relationship to device or procedure, that: led to a death, 	

Table 8-1 Definitions of Adverse Event (AE) Types, Device Deficiency

	led to a serious deterioration in health that either:		
	 resulted in a life-threatening illness or injury, or 		
	 resulted in a permanent impairment of a body structure or a body function, or 		
	 required inpatient hospitalization or prolongation of existing hospitalization, or 		
	 resulted in medical or surgical intervention to prevent life threatening illness or injury or permanent impairment to a body structure or a body function. 		
	 led to fetal distress, fetal death or a congenital abnormality or birth defect. 		
	• Other serious important medical events. Report when the event does not fit the other outcomes, but the event may jeopardize the patient and may require medical or surgical intervention (treatment) to prevent one of the other outcomes.		
	Examples of procedure related serious AEs (SAEs) may include: stiffness requiring manipulation of the hip under anesthesia, dislocation of hip requiring closed reduction, Deep Vein Thrombosis (DVT) without hospitalization. Examples of device related SAEs may include radiolucent lines around the femoral component or joint dislocation.		
	All serious adverse events should be reported to the Sponsor by completing an		
	AE eCRF as quickly as possible – not to exceed 72 hours after the investigator or		
	site becomes aware of the event		
Device Deficiencies	Are defined as inadequacy of a medical device with respect to its identity, quality, durability, reliability safety or performance. Device deficiencies include		
	malfunctions, use errors and inadequate labeling. Upon identification of device		
	appropriate therapeutic and follow-up measures in accordance with good modical		
	propriate therapeutic and follow-up measures in accordance with good medical actice and notify the IRB as applicable. The Investigator must document follow-treatment of any resulting AE (if applicable) and the Sponsor will report the		
	event through its applicable complaint reporting channels.		

8.2 Definition of Severity

An adverse event (AE) or an adverse device effect (ADE) may be:

- Mild: Easily tolerated and transient in nature with minimal or no impairment of normal activity)
- Moderate: Poorly tolerated, sustained and interferes with normal activity and requires medical attention
- Severe: Poorly tolerated, requires intervention and significantly affects activities of daily life; or
 places the Subject at immediate risk or harm.

8.3 Device or Procedure Related

The determination whether the AE is related to the device or procedure will be based upon whether a causal relationship between the device or procedure and the AE is at least a reasonable possibility, *i.e.* the relationship cannot be ruled out. A causal relationship cannot be ruled out if, in the medical judgment of the Investigator, the effect follows a reasonable temporal association with the use of the device and/or is confirmed by the improvement of the effect upon discontinuation of the clinical use of the device, and/or the effect is not reasonably explained by the Subject's clinical state.

Relationship to study device or procedure should both be rated as follows, "*Is this event related to the study device (or procedure)?*" options are: Definitely, Probably, Possibly, Remote possibility or Definitely not. All adverse events (medical change from baseline) experienced by a subject should be noted in their source documents with these relationships to document the sites' determination.

8.4 Worsening Adverse Events

For a worsening AE, the original AE should be reported as resolved on the AE eCRF and an additional AE eCRF should be completed for the new Severity. Examples of this exercise are provided in the study tool "Case Report Form Completion Guidelines", provided separately. An example is that if a "Mild" AE of pain with no treatment exacerbates to a "Moderate" AE of pain with a treatment of an injection, a study site must resolve the "Mild" AE and report the worsening on an additional AE eCRF. The original 'Mild" AE will not be counted twice; however, each AE will be counted individually – as in one Mild AE and one Moderate AE.

8.5 Safety Reporting Timelines

Each reportable adverse event should be forwarded to the Sponsor via submission of the AE eCRF. It is expected that each adverse event will be submitted when the site becomes aware of the event as defined in Section 8. See the table below for the maximum timelines for reporting:

АЕТуре	Reporting Timelines
Serious Adverse Events (SAEs)	Completion of an AE eCRF as soon as the site becomes aware,
	but not longer than 72 hours after date of awareness
All other non-serious AEs that are	Submission of AE eCRF within 2 weeks of date of awareness
reportable per this protocol	

Confidential Version Date: 040CT2021

8.6 Exacerbation of Pre-existing Medical Conditions

Pre-existing medical conditions or symptoms reported prior to device implantation are to be recorded as history and not to be recorded as AEs (e.g., History of Asthma or existing osteoarthritis in contralateral knee would be recorded on the Subject History eCRF). In the event there is an exacerbation of the pre-existing medical condition or symptoms that meets the definition of serious, then an AE must be reported (e.g. exacerbation of existing Asthma that requires hospitalization).

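### Protocol Section 8.6, on its natural reading, makes worsening of a pre-existing condition reportable only if serious, which conflicts with Section 8 for non-serious device- or procedure-related worsening

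*Protocol*

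**What the plan says.** The opening text of Protocol Section 8 includes in its AE definition "untoward clinical signs (or change or worsening of a pre-existing medical condition) in a patient", with no seriousness threshold. Table 8-1 repeats that definition. Section 8 then states that "there are three types of events that will need to be reported via the Adverse Events (AE) eCRF". The first class is "Device Related AEs (see Section 8.3 and Figure 8-1 below", the second is "Procedure Related AEs (see Section 8.4 and Figure 8-1 below", and the third is serious AEs. Section 8.5 sets a deadline for reportable events that are not serious: "Submission of AE eCRF within 2 weeks of date of awareness".

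Section 8.6 deals with conditions that predate surgery. Its general rule is: "Pre-existing medical conditions or symptoms reported prior to device implantation are to be recorded as history and not to be recorded as AEs". Its next sentence covers an "exacerbation of the pre-existing medical condition or symptoms that meets the definition of serious, then an AE must be reported". The examples are asthma and osteoarthritis of the opposite knee. The section says nothing about relationship to the device or procedure, and does not set the study hip apart.

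SAP 8.9 summarises AEs on the Safety set, overall and by device relationship, procedure relationship and seriousness, and lists the AEs that were reported.

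**The concern.** Patients coming to hip replacement commonly have hip symptoms already, and the pre-operative hip evaluation form records groin and buttock pain (SAP 8.8.8). Suppose such a symptom becomes worse after surgery, is not serious, and the investigator rates it as procedure related. A site following Section 8 completes an AE eCRF. A site following 8.6 can treat the event as history and complete none. The same complaint in a subject without that symptom before surgery would be reportable under either section.

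At stake is whether the AE eCRF, and the Safety-set tables built on it, apply one rule across up to 20 sites. This matters because the trial has no data monitoring committee (SAP Section 9), and Protocol 8.8 bases the sponsor's risk review on what is reported.

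**Working it through.** No arithmetic applies; this is a comparison of rules. Take worsening of a condition or symptom that was present before implantation, and classify it by seriousness and by relationship to device or procedure.

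| Worsening of a pre-existing condition | Section 8 | Section 8.6, natural reading | Result |
|---|---|---|---|
| Serious, related | Report | Report | Agree |
| Serious, unrelated | Report | Report | Agree |
| Non-serious, unrelated | Do not report | Do not report | Agree |
| Non-serious, related | Report (class 1 or 2) | Do not report | **Conflict** |

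The conflict is confined to the last row.

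**Why the natural reading of 8.6 is restrictive.** Its general rule takes pre-existing conditions and symptoms out of AE recording, and its next sentence names a single case that comes back in. Every serious AE is already reportable under class 3 of Section 8. If 8.6 did not limit reporting to serious exacerbations, that second sentence would add nothing.

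**Whether another section settles it.**
- Section 8.1 and Exhibit A exempt listed immediate post-operative events, up to 24 hours or up to discharge, and restore reporting when severity exceeds what is expected or the event is serious. They give no rule for a hip symptom that worsens weeks later.
- Section 8.3 defines relatedness and keeps all AEs in source documents. It does not say which of them override 8.6.
- Section 8.4 covers worsening of an event already reported as an AE, not of a pre-operative symptom.
- Section 8.5 confirms that some non-serious AEs are reportable, but not which.
- SAP 8.9 works from the AEs collected and does not address the question.

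**What is still captured.** Groin and buttock pain are summarised before surgery and at 6 and 24 weeks (SAP 8.8.8), as is the Harris Hip Score (SAP 8.8.5). These summaries use the Per Protocol set and carry no relatedness or AE severity rating. Thigh pain is absent because the form does not collect it (SAP Section 10).

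**Size.** The documents give no rate for non-serious related exacerbations, so the number affected cannot be derived. For scale only, each 1% of the 400 planned subjects is 0.01 × 400 = 4 subjects.

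**The case against.** The strongest reply is that 8.6 never uses the word only. Its first sentence can be read as sending the pre-existing condition itself to history, which nobody disputes, and its second as giving a sufficient condition for reporting. Both examples concern conditions unrelated to the study hip, where 8.6 and Section 8 agree. The protocol also repeats itself elsewhere (the 72-hour rule for serious AEs is in both Table 8-1 and 8.5), so a redundant sentence is not decisive. A site may also regard post-operative groin pain as a new event. Finally, Section 8 points to Figure 8-1 for all three classes, and neither that figure nor the separate CRF Completion Guidelines was available.

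Much of this stands. The restriction is implied, not stated, and the unseen sources may give sites a clear instruction. But the examples are only illustrations, and the rule itself covers conditions and symptoms in general. Even if Figure 8-1 sides with Section 8, the written sections would still need to agree.

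A reader might infer several stronger points that the documents do not support:
- **That worsening hip symptoms are hidden.** This could apply to the AE eCRF and AE tables, but not to the hip scores, pain items or source documents.
- **That reported AE counts are too low.** Nothing shows how sites read 8.6 or how often the disputed event occurs.
- **That the 90-day complication summary loses the same events.** The protocol does not define complications as AE eCRF entries.
- **That the example in 8.4, a moderate "AE of pain with a treatment of an injection", proves the point.** It shows that treated, non-serious pain can be reportable, but it concerns an event already reported as an AE.
- **That the arms are affected differently.** Allocation is in blocks of 4 from stickers supplied to each site (Protocol 3.4, SAP Section 3), so a site's habitual reading would fall on both arms. Sites do know the assignment after randomization, but the documents do not show that this alters reporting.

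**Conclusion.** The concern holds in a limited form. On its natural reading, 8.6 conflicts with Section 8 and Table 8-1 for non-serious exacerbations that the investigator rates as device or procedure related, including those of the study hip. These events may be absent from the AE eCRF and from the SAP 8.9 tables. For the other combinations of seriousness and relationship the sections agree.

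The conclusion rests on reading 8.6 as restrictive, and is subject to Figure 8-1 and the CRF Completion Guidelines, which could not be checked. The number of events is unknown. The AE analyses are descriptive and the primary endpoint is unaffected. The point should be corrected because the remedy is small and concerns the completeness of safety data.

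**What to change.** Reconcile 8.6 with Section 8. State that an exacerbation of a pre-existing condition or symptom is reported on the AE eCRF if it is serious or if the investigator rates it as device or procedure related under 8.3. Say that the exemption in 8.1 and Exhibit A continues to apply only to the immediate post-operative events listed there, so that it is not used as a benchmark for later symptoms.

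Check that Figure 8-1 and the CRF Completion Guidelines give the same rule, change them only if they do not, and notify sites. In the same amendment, correct the cross-reference in Section 8: the procedure-related class points to 8.4, which is about worsening AEs, whereas relatedness to the procedure is defined in 8.3.

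The cost is a short protocol edit and a site notice. The downside is a modest rise in reported non-serious AEs.

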8.7 Determination of Anticipated/Unanticipated

The PI is responsible for determining whether an AE is **anticipated** or **unanticipated**. This determination is based on whether the severity, type and frequency of the AE is consistent with the Instructions for Use (IFU), in the opinion of the PI. Note that since THA is a routine elective procedure, the vast majority of adverse events are anticipated and included in the IFU.

When a PI classifies an AE as unanticipated, the Sponsor will a review the determination based on the reported event and in consideration of the IFU and internal risk reports. In the event that the Sponsor has a different opinion on the determination a query will be generated. When there is a discrepancy on the determination between the site and the Sponsor, both opinions will be recorded and reported as required to the relevant IRB.

8.8 Minimization of Risks

The Sponsor will further minimize the identified and/or emergent risks throughout the study by reviewing the reported complications and adverse effects. Adverse events will be reviewed and reported as applicable based on IRB and regulatory requirements. Based upon an evaluation of such events, the Sponsor may either amend the investigational plan or terminate the investigation to protect the rights, safety and welfare of the study Subjects.

Should an IRB decide to suspend or withdraw its approval for a PI to conduct the study at that institution, based on unacceptable risks to the study Subjects, the study Sponsor will notify all reviewing IRBs, and PIs of this action. To further minimize risks, any new information obtained during the course of the study relating to unanticipated adverse findings will be provided to all Subjects, PIs, and IRBs.

The study has been designed to minimize the number of Subjects yet provide sufficient numbers of Subjects for valid scientific analysis of the compiled study data. The study design, the procedures for monitoring and the documentation, reporting and evaluation of the results will further control risks.

Figure 8-1: AE Reporting Flowchart

The AE Reporting flowchart illustrates a series of questions a site must consider when determining whether a clinical observation must be reported, and which AE's do not need to be reported for this CIP per the required timelines as defined in Section 8.5.

9 Informed Consent Process

In compliance with ISO 14155 and 21CFR50, no Subject shall be enrolled in an investigation without provision of adequate informed consent. The Principal Investigator is responsible for ensuring that no Subject is included in the study without adequate informed consent being provided. Failure to obtain and properly document this process is in violation of 21CFR Part 50, ISO 14155, the Declaration of Helsinki, and this study protocol.

All Informed Patient Consent (IPC) documents must have favorable opinion of the IRB. Many institutions request modification of the IPC to satisfy specific institutional requirements. The use of a modified or unique IPC is permitted provided that all applicable regulatory requirements are met and the document is approved by the Sponsor before use.

Subjects who agree to participate in the study will complete an IRB approved IPC document that documents his or her willingness to take part in this study. Each potential Subject will have the nature and the purpose of this study explained to him or her by the Principal Investigator (PI) or another delegated member of the investigative team at the study Site. The PI or designee will explain the following features of the study to the patient thoroughly and will offer to answer any questions the patient may have.

- The purpose of the study
- The potential risks or adverse events that are posed by their treatment
- The potential risks or adverse events related to study participation
- Alternative procedures/treatments available to the Subject
- Requirements of the study follow-up visits
- All of the Subject's rights as a participant in the clinical investigation

Consent must be given by the Subject and documented on an Informed Patient Consent Document in the primary language of the Subject. A signed copy of the IPC is to be provided to the Subject. An IPC must be obtained for all Subjects prior to the Subject completing any study-specific assessments or procedures that are not standard of care. A study Subject is considered enrolled in the study once they have signed the IPC.

No dates should be pre-populated or completed by someone other than the person providing the signature.

Subjects will be made aware that their personal data will be collected and processed in accordance with data protection legislation including Health Insurance Portability and Accountability Act of 1996 (HIPAA). The release of Personal Health Information (PHI) for the purpose of this clinical investigation will be included in the informed patient consent unless site policies require this release be maintained in a

Confidential Version Date: 040CT2021

DePuy Synthes Protocol DSJ_2019_03 / Version 2.0 / TV-eFRM-02920 Page **31** of **53** separate document. Results from this clinical investigation may be published, however, subject confidentiality will be maintained at all times and it will not be possible to identify them from any data presented.

Any data collected for subjects for whom consent cannot be recognized will not be reported. In such a case the subject will be excluded from all analysis sets (enrolled, safety, per protocol).

10 Statistical Methodology

Statistical analysis will be performed using SAS[®]software version 9.4 or higher. Any further software that may be necessary will be described in the final study report.

